20.0 Compensation for Research-Related Injury

20.1 *N/A*

20.2 *N/A*

21.0 Economic Burden to Subjects

21.1 *N/A*

22.0 Consent Process

22.1 *Indicate whether you will you be obtaining consent, and if so describe:*

- *Consent process will take place in the College of Medicine and/or at Vascular Surgery Associates.*
- *Patients must first have doctor's approval prior to second visit and consent.*
- *Every week we will speak with patients and make sure they are comfortable and without any distress.*
 - *We will be following the HRP-090 consent process.*

Non-English Speaking Subjects

- *Non-English patients will be excluded from the current study due to inability to translate.*

Waiver or Alteration of Consent Process (consent will not be obtained, required information will not be disclosed, or the research involves deception)

- *N/A we will obtain consent.*

Subjects who are not yet adults (infants, children, teenagers)

- *N/A*

Adults Unable to Consent N/A

23.0 Process to Document Consent in Writing

- 23.1 *We are using the common consent form for patients.*
- 23.2 *We will obtain written consent and then doctor's approval of PAD patients. All healthy volunteers will not be required to get physician approval but will also document consent in writing.*

24.0 Setting

- 24.1 *Subjects with PAD will be identified and recruited from Vascular Surgery Associates Clinic. Screening visit for healthy volunteers will take place at FSU College of Medicine. Study procedures (for all subjects) for Visit 2 and 3 will be conducted at FSU College of Medicine facilities.*
 - *For research conducted outside of the organization and its affiliates describe: N/A*

25.0 Resources Available

- 25.1 *Describe the resources available to conduct the research: For example, as appropriate:*
 - *Given that the percent of individuals over 60 years of age with PAD is 12-20% we believe this allows us with a sufficient pool of individuals to recruit in the Tallahassee area.*
 - *80% of [name], 10% of [name] and 15-20% of [name] time will be committed to this study.*
 - *Our space for human research is approximately 1000 sq feet. We have access to patient rooms in the MRI facility where we are conducting part of the current study. This room is outfitted with chairs and an examination table we will use for resting measurements. We are currently using these facilities on another human study with splints and muscle stretching. Down from the MRI room we have access to a hallway where we will conduct the 6MWT.*
 - *We are located within the College of Medicine and will have an AED close by. In addition, we will have a College of Medicine physician ([name]) that will have oversight of the study. He will not directly interact with patients; however, he is aware of the protocols being followed.*
 - *All individuals will be trained to understand data collection and methods prior to first patients with mock run throughs to ensure that all research runs accordingly and will be the primary individual taking measurements.*

26.0 Multi-Site Research* -- N/A

Cover Page

Study Title: Creatine Use and Muscle Stretching in Peripheral Artery Disease

NCT Number: NCT04471792

Date of Statistical Analysis Plan: 04-02-2022

Statistical Analysis Plan to follow

PAD- Stretching +Creatine Statistical Analysis

The primary goal of this study is to determine the effects of splint-based passive muscle stretching with and without creatine monohydrate supplementation protocol on changes in microvascular function, walking performance, and subjective measures of walking performance in PAD patients. Based on data from Moraes et al. [129] who reported a 10% increase in post-occlusive reactive hyperemia in participants taking creatine (effect size: 0.78, mean 1: 0.54, mean 2: 0.49, pooled SD 0.02), a sample size of 9 participants per group was needed to detect changes in microvascular reperfusion variables with 80% power and an α of 0.05. Descriptive statistics were calculated for all variables and included means and standard deviations for normally distributed continuous variables and medians, minima and maxima for non-normally distributed continuous variables. Independent t-tests were used to determine if there were differences in baseline variables between groups. If baseline values between groups were significantly different, a secondary analysis was conducted using an analysis of covariance with baseline values as covariates. If sphericity was violated ($\varepsilon < 1$), a Greenhouse-Geisser correction was used. Changes in dependent variables over time were analyzed using repeated measures ANOVA (group by time). When interactions were significant, independent and paired t-tests were used to determine where differences were located. If there were no differences in measured variables between creatine and placebo supplementation, data were pooled, and paired t-tests were used to evaluate pre to post differences in the measured variables of microvascular function, walking performance, and subjective measures of walking performance. Pearson Product Moment Correlations were completed on baseline variables to look at relationships between microvascular function, walking performance, and subjective measures of walking performance. All significance was accepted at $p < 0.05$. Statistical outliers were removed if they exceeded 2 standard deviations from the baseline mean or mean changes from pre to post-intervention. All analyses were performed using the SPSS 27 statistical package.

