2.0 Objectives*

- 2.1
 1. To utilize near-infrared spectroscopy to investigate if our research device for stretch training, and creatine loading impact cardiovascular performance in aged and PAD patients.
 2. To characterize near-infrared spectroscopy derived tissue oxygenation responses at rest and during a walking test (i.e., six-minute walk test). We will also assess parameters with Magnetic Resonance Imaging.
- 2.2 It is hypothesized that the stretching protocol will improve both NIRS derived tissue oxygenation and magnetic resonance derived leg blood flow measures and that creatine supplementation will further improve phosphorus metabolite muscle performance. All patients will undergo either 4 weeks of stretch training with- or-without creatine supplementation according to previously defined creatine guidelines (Sanchez-Gonzalez et al 2011).

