6.0 Procedures Involved*

- 6.1 All patients (PAD or healthy volunteers) will undergo 4 weeks of splint stretching (30min/day; 5days/week – procedures attached with this submission) and be randomized into groups with or without creatine supplementation (10g/day for the first 5 days and 5g/day for the remainder). Placebo supplementation (Fiber powder; cellulose) will be given during the opposite arm of the study and according to section 6.2 (below).
- 6.2 Each potential patient/participant will be screened to determine potential eligibility by the research team. If the individual is eligible, see inclusion/exclusion criteria, they will be asked to consider joining the study. Individuals meeting the initial criteria and who agree to participate in the study will sign informed consent and complete any medical history forms. All participants must abstain from alcohol for 24 hours and caffeine/food for ~ 4 h prior to testing sessions. The current investigation is a randomized single-blind study design.
 - C1. Health and exercise questionnaires: Subjects' medical history and exercise habits will be

PROTOCOL TITLE: Creatine supplementation and muscle stretching in peripheral artery disease patients

assessed by self-reported health and exercise questionnaires: demographics and health history (Visit 1), physical activity readiness (Visit 1), health survey-SF36 (Visit 2 and 3), international physical activity questionnaire (I-PAQ, Visit 2 and 3), walking impairment questionnaire (WIQ, Visit 2 and 3).

- C2. Fitbit: Subjects will be given a Fitbit Charge 2 (Fitbit, San Francisco, California) to wear for a 1 week period starting at Visit 1 and Visit 3 to measure daily step count before and after the intervention. At this time, we anticipate 4-8 subjects with PAD using a Fitbit during the course of the study. We will recruit 2-4 PAD patients to serve as time controls and not partake in the intervention.
- C3. 'Anthropometric measurements and vitals will consist of subject height measured on a stadiometer and weight measured on a calibrated scale, heart rate (resting) and baseline blood pressure after 10-min of quite supine rest. Next, we will measure circumference of the waist and lower leg and range of motion of the knee and ankle. All of these measurements will be done at Visit 2. *Resting heart rate and blood pressure will be repeated at Visit 3.*

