C6. ‘Cardiovascular assessment’ will be measured via the “6-minute walk test (6MWT)” (Visit 2 and Visit 3) a sub-maximal clinically relevant test to assess efficacy of the 4-week intervention. All patients/participants will undergo a 6MWT pre/post intervention. Briefly, a standardized model will be followed according to American Heart Association guidelines. The 6MWT will be performed on a level surface by a research team member. Patients will be instructed to cover the greatest distance they can in 6-minutes at a pace of their choosing. Chairs will be placed periodically along the hallway in case a patient, or participant, needs to rest until they can begin again. The 6MWT data collection form and corresponding rating scales are provided with this submission.

- C7. “Physical function” will be measured via the 8 foot up and go, 30 second chair rise, and chair sit and reach tests. The 8 foot up and go requires the subject to start in a seated position, stand up, walk 8 feet, then return to the seated position. The score for this assessment will be the number of seconds needed to complete this task. The subject will perform this assessment twice, and the best score of the two trials will be used. Next, the subject will perform the 30-second chair stand test. In this assessment, the number of full stands from a seated position will be counted in the 30-second time period. The chair sit and reach will require the subject to reach his/her fingertips towards a straightened leg from a seated position. This assessment will be performed three times on each leg. The score will be the number of centimeters between the fingertips and toes for each leg.
- C8. “Muscle oxygenation characteristics” of the lower leg (i.e., gastrocnemius and soleus) will also be evaluated via NIRS with a heel raise test. The subject will complete heel raises for a 1 minute period while we continuously monitor muscle oxygenation during exercise and recovery.

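### Every randomised subject stretches, so the trial can test creatine added to stretching, but the pre-post change in the SAP cannot show what stretching itself does

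*SAP*

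**What the plan says.** **The question.** The SAP's primary goal is to "determine the effects of splint-based passive muscle stretching with and without creatine monohydrate supplementation protocol on changes in microvascular function", and also on walking performance and subjective walking measures, in PAD patients. Protocol 2.2 states a hypothesis about stretching alone: "the stretching protocol will improve both NIRS derived tissue oxygenation and magnetic resonance derived leg blood flow measures", with creatine expected to add to that.

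**The design.** Protocol 6.1: "All patients (PAD or healthy volunteers) will undergo 4 weeks of splint stretching". The same sentence has them "be randomized into groups with or without creatine supplementation". Creatine is the only randomised factor. Healthy volunteers stretch too, and the MRI subgroups in C5.A are healthy or PAD by placebo or creatine, so neither supplies a stretch-free group.

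**The one stretch-free group.** Item C2 (Fitbit) says: "We will recruit 2-4 PAD patients to serve as time controls and not partake in the intervention". This is the only mention of time controls in either document.

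**The analysis.** The SAP uses a repeated measures ANOVA with group and time. Within-arm and between-arm t-tests follow a significant interaction. If creatine and placebo do not differ, the arms are pooled and pre-post differences are tested with paired t-tests. The SAP names only the creatine and placebo groups.

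**The concern.** A before-after change in people who all stretch contains whatever stretching does plus whatever would have happened anyway over four weeks. For the 6-minute walk, that includes familiarity with a repeated test. For the SF-36, IPAQ and WIQ, it includes the expectations of people who know they are being treated and who hear from staff every week. The creatine-placebo difference removes such influences when they are common to both arms. A time effect or a pooled paired test does not.

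The pooled test comes into play exactly when creatine shows no difference, which is when the stretching change is likely to become the main result. A report could then credit stretching with an improvement that is wholly non-specific, and nothing in the SAP warns against that.

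**Working it through.** **Step 1. What each contrast contains.** Let S be the true stretching effect, N the non-specific change between visits, and C the added effect of creatine. With equal arms:

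| Quantity | Content |
|---|---|
| Change in placebo arm | S + N |
| Change in creatine arm | S + N + C |
| Creatine minus placebo (group-by-time) | C |
| ANOVA time effect, or pooled pre-post change | S + N + C/2 |

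Only C is separated from everything else. No quantity in the SAP separates S from N; that needs a group whose change is N alone.

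**Step 2. Size of the problem for the pooled test.** The plan gives no figure for the stretching question, so there is none to reproduce. Its 9 per group was derived from creatine data and is used here only as an input.

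- Pooled n = 2 × 9 = 18 (SAP).
- α = 0.05 (SAP). Sidedness is not stated; two-sided is assumed.
- S = 0 and C = 0 (assumed, to isolate false attribution).
- N = 0.25, 0.375 or 0.5 SD of change (assumed; the documents give no value).

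Noncentrality = N × √18 = N × 4.243. Critical value t(0.975, 17 df) = 2.110. Rejection rates come from the noncentral t distribution.

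| N (SD of change) | Noncentrality | P(significant) |
|---|---|---|
| 0 | 0 | 5% |
| 0.25 | 1.061 | 17.0% |
| 0.375 | 1.591 | 32.4% |
| 0.5 | 2.121 | 51.6% |

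The ANOVA time effect has the same noncentrality on 16 rather than 17 df and needs no pooling condition, so it behaves almost identically.

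**Step 3. Apply the SAP's condition for pooling.** With C = 0, the arms show no significant difference in about 95% of trials. The chance that pooling happens and the pooled test is significant is then about:

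- 0.95 × 17.0% = 16%
- 0.95 × 32.4% = 31%
- 0.95 × 51.6% = 49%

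Simulation of the sequence with 9 per arm gives the same three figures.

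**Step 4. Could the time controls supply N?** The 95% confidence half-width for their mean change, in SD of change, is t(0.975, n−1)/√n:

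- n = 2: 12.706/1.414 = 8.98
- n = 4: 3.182/2 = 1.59

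For 18 stretchers against 4 time controls: 2.086 × √(1/18 + 1/4) = 2.086 × 0.553 = 1.15.

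Even in the best case, the comparison could not distinguish an effect of 0.5 SD, or even 1 SD, from none. A formal test would not rescue the inference.

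**The case against.** **Creatine is the real question, and it is controlled.** Protocol 3.2 treats the benefit of stretching as shown by the group's earlier work and asks whether a supplement adds to it. The primary objective in the study summary concerns stretching combined with creatine, and 5.1 calls this a pilot. The SAP goal can be read as the same contrast. This stands, and it limits how serious the point is. It does not remove the point, because 2.2 states a separate hypothesis for stretching and the SAP goal speaks of its effects.

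**The SAP does not claim that the pooled test isolates stretching.** Correct: it speaks only of pre-to-post differences. The causal reading comes from the goal and from 2.2, so the correction belongs in the goal and in reporting.

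**The sources of non-specific change are partly conjecture.** This also largely stands. Entry is by ankle-brachial index or clinical diagnosis with a stable condition (10.1), not by poor outcome values, so regression to the mean is a weak candidate. Walk learning and questionnaire expectation do not obviously carry over to the resting cuff-occlusion NIRS measure.

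**Stronger readings that a reader might infer, and that the documents do not support:**

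- *That the placebo-arm paired test is an equally common route to a false stretching claim.* The SAP runs within-arm t-tests only after a significant interaction. In simulation with the same shifts, a significant placebo-arm test is reached in about 2% of trials with no creatine effect, and 1-4% with a creatine effect of 0.78 SD.
- *That there was no practice walk.* C6 is silent on this; it refers to a guideline-based procedure and a form that are not in these documents.
- *That the time controls are known to be non-randomised.* C2 says only that they are recruited; no randomisation to that group is described.
- *That the time controls have no outcome data.* C6 says "All patients/participants will undergo a 6MWT pre/post intervention", and 9.1 asks all subjects to attend three visits. They may well be covered.

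**Conclusion.** The point holds for stretching only. The plan poses a question about the effect of stretching, gives stretching to every randomised subject, and analyses it through pre-post change with no stretch-free comparator. That follows from the documents and needs no numerical assumption.

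The size does need one. A false stretching finding in about 17-52% of trials (16-49% through the pooling rule) rests on an assumed non-specific shift of 0.25-0.5 SD of change, no true effect of stretching or creatine, 18 pooled subjects and two-sided testing. The range is more plausible for the 6-minute walk and the questionnaires than for resting NIRS.

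The randomised creatine-placebo comparison is unaffected. This is therefore a limit on what may be concluded, worth correcting before results are reported, and not a defect that undermines the trial.

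**What to change.** 1. **SAP goal and reporting.** State that causal claims are limited to creatine versus placebo on a background of stretching. Label the ANOVA time effect and any within-arm or pooled pre-post result as uncontrolled change that cannot be attributed to stretching. This costs a few sentences and remains possible although the SAP is dated 2022 and written in the past tense.

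2. **Time controls.** Say in the SAP whether they were recruited and measured at Visits 2 and 3. If they were, list their individual changes beside those of the stretched groups, descriptively and without a test. No new visits are asked for: the protocol expected primary analysis by summer 2021, so data collection may already be over.

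3. **Reconcile 6.1 with C2.** One says that all patients stretch; the other describes PAD patients who do not take part in the intervention.

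The price is a weaker statement about stretching. No subjects, measurements or tests are added.

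### The SAP's 9 per group at 80% power cannot be reproduced from its printed inputs; it needs assumptions the SAP does not state

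*SAP*

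**What the plan says.** The SAP is one continuous section. Its sample-size sentence cites a published creatine study and prints the inputs as "effect size: 0.78, mean 1: 0.54, mean 2: 0.49, pooled SD 0.02". It concludes that "a sample size of 9 participants per group was needed to detect changes in microvascular reperfusion variables with 80% power", at an α of 0.05.

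It does not give the type of effect size (d, paired d, f or r), the test behind the calculation, its sidedness, a pre-post correlation, or whether the two means are arms or visits.

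The main analysis is given as "Changes in dependent variables over time were analyzed using repeated measures ANOVA (group by time"). The SAP then acts on a null creatine result: "If there were no differences in measured variables between creatine and placebo supplementation, data were pooled, and paired t-tests were used".

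The protocol has no prospective calculation. Section 12.1 aims for 20 PAD patients and 20 healthy volunteers without a power basis. Section 17.1 calls the study a pilot and defers the power analysis until the data are in.

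**The concern.** A sample-size statement should let a reader recover n from the printed inputs. Here the two visible routes, the 0.78 and the means with their SD, give answers that differ about sevenfold (27 against 4 per group), and neither is 9.

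The stake is how a null creatine result will be read. A reader who accepts the 80% will take non-significance as fair evidence that creatine adds nothing to stretching, and the pooling rule does the same in the analysis itself. If the 80% applies to an effect nobody can identify, the reader cannot tell which creatine effects a null result makes unlikely.

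**Working it through.** **Inputs (SAP):** effect size 0.78; means 0.54 and 0.49; SD 0.02; 80% power; α = 0.05; 9 per group. **Assumed because not stated:** two-sided test and 1:1 allocation. Sample sizes use the exact noncentral t or F distribution.

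**1. Standardised difference from the printed means and SD**
- d = (0.54 − 0.49)/0.02 = 2.5.
- Rounding limits: (0.535 − 0.495)/0.025 = 1.6 and (0.545 − 0.485)/0.015 = 4.0.

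**2. How 0.78 relates to this**
- As a correlation: r = d/√(d² + 4) = 2.5/√10.25 = 0.781. The printed inputs then agree with each other.
- As Cohen's d: the SD would have to be 0.05/0.78 = 0.064, about three times the printed value.

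**3. Trying to reproduce 9 per group**

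| Reading | n for 80% power, two-sided | one-sided | Power at 9, two-sided |
|---|---|---|---|
| d = 2.5, two-sample | 4 per group | 3 | 99.9% |
| d = 1.6 (rounding limit) | 8 per group | 6 | 89% |
| d = 4.0 (rounding limit) | 3 per group | 2 | over 99.9% |
| d = 0.78, two-sample | 27 per group | 22 | 34% |
| 0.78 as a paired effect | 15 | 12 | 54% |
| f = 0.78, two-group ANOVA | 8 per group | n/a | 87% |

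None gives 9. If 0.78 is r, the matching two-group comparison is the d = 2.5 row.

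**4. What would give 9 in a two-sided two-sample t-test**
- The detectable d at 80% power is 1.507 with 8 per group and 1.407 with 9, so 9 is the minimum only for d between these values.
- For a difference of 0.05 that means an SD of 0.05/1.507 = 0.033 to 0.05/1.407 = 0.036. A printed 0.02 can stand for at most 0.025.

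**5. Routes to 9 that need an unstated input**
- *Change score, 0.78 in single-visit SDs:* d = 0.78/√(2(1 − ρ)). The minimum is 9 only for ρ of about 0.85 to 0.865. Power at 9 per group is 34% at ρ = 0.5, 52% at 0.7, 69% at 0.8 and 81% at 0.85.
- *Group-by-time interaction with f = 0.78/2 = 0.39:* λ = f²·N·2/(1 − ρ), with 1 and N − 2 degrees of freedom. N = 18 is the minimum only for ρ of about 0.39 to 0.46. At ρ = 0.5 it is 8 per group, and 9 per group gives 87%.
- *Change score at the rounding limit d = 1.6:* the minimum is 9 for ρ of about 0.354 to 0.436.

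**6. What 9 per group delivers on any reading**

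For the between-arm difference in change, in SDs of the change:
- 80% power at 1.41 SD.
- 95% CI half-width = t(0.975, 16)·√(2/9) = 2.120 × 0.471 = 1.0 SD.
- Chance of a non-significant result (1 − power): 83% at a true 0.5 SD, 49% at 1.0 SD, 20% at 1.41 SD.

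If the pooling condition means a non-significant group-by-time interaction at 0.05 (an assumption), these are also the chances that a single variable meets it.

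**The case against.** The best defence is that this is incomplete reporting and not an error. The inputs agree if 0.78 is r. Some assumption sets give exactly 9, and several others come within one participant per group: f = 0.78 in a two-group ANOVA, the rounding limit d = 1.6, and f = 0.39 with a correlation of 0.5 in the SAP's own repeated measures analysis all give 8. On that last route, 9 per group has at least 80% power at any correlation from about 0.39 upward. In addition, the study is a self-described pilot, 20 PAD patients would give about 10 per arm under 1:1 allocation, and nothing shows that the 9 set enrolment. The non-significance rates in step 6 follow from n = 9 alone and would be the same had the calculation been fully documented.

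Much of this stands. No direction of error can be claimed, and neither 27 nor 4 can be called the correct n. But each near-miss still needs an effect-size type or a correlation that the SAP does not give, and the near-misses disagree about what 0.78 means. The f = 0.78 reading also conflicts with the printed means and SD, which imply f = 2.5/2 = 1.25. The step 6 figures do not show that the calculation is wrong. They show why the missing specification matters, because the SAP makes a decision on a null result.

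**Conclusion.** The concern holds. The stated 9 per group at 80% power follows from no direct reading of the printed inputs, and it cannot be reproduced without adding assumptions.

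The size of the discrepancy depends on the reading. If the SD of 0.02 is right, 9 is more than enough for the cited effect: 99.9% power, and still 94% as a change score at zero correlation (d = 2.5/√2 = 1.77, n = 7). If 0.78 is a standardised mean difference in a two-sample comparison, power is 34%. The documents cannot settle which applies, so this is not a finding that the trial is underpowered.

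What does not depend on the reading is that 9 per group detects a difference in change of about 1.41 SD with 80% power and estimates it to within about 1.0 SD. A null creatine result is therefore weak evidence against moderate effects. These figures assume a two-sided test at 0.05, equal groups and approximately normal change scores.

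**What to change.** In the SAP's sample-size paragraph:

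1. Check 0.78, the two means and the SD against the cited source, and correct whichever is wrong.
2. State the effect-size type (d, paired d, r or f), whether the means are arms or visits, the test, its sidedness and any pre-post correlation used.
3. Correct n or the stated power to match. Quote 34% only if 0.78 is confirmed as a standardised mean difference in a two-sample comparison, or in change scores with correlation 0.5.
4. Whichever reading is confirmed, add that 9 per group gives 80% power for a between-arm difference of about 1.41 SD of the change, with a 95% CI half-width of about 1.0 SD.

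In the analysis paragraph, require the creatine-minus-placebo difference in change to be reported with its estimate and 95% CI for each variable, including where the arms are pooled. State that non-significance is not taken as evidence of no difference.

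The cost is SAP wording and a few extra reported intervals, with no added patients or visits. The stated power may look less favourable if 0.78 proves to be a standardised mean difference.
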